10. STUDY TREATMENT MANAGEMENT

Study treatment (PFS or autoinjectors) must be stored in a secure location. Accountability for study treatment is the responsibility of the Investigator. Study treatment must only be dispensed by a Pharmacist or medically qualified staff, and stored in a secure, monitored, locked location in accordance with the conditions specified in current prescribing information or the Directions for Handling and Administration (DHA) included in the Study Reference Manual.

Study treatment is to be dispensed only to subjects enrolled in this study. Once treatment is dispensed to a subject, it can only be used by that subject.

10.1. DAC HYP

Prefilled Syringe

DAC HYP is supplied as a liquid in a 1-mL BD-staked PFS with a 29 gauge \times ½ inch needle, comprising 150 mg/mL DAC HYP plus excipient materials (sodium succinate, sodium chloride, and polysorbate 80). At a minimum, the study treatment label will include a study reference code, drug identifier, quantity of dosage units, lot number, and other pertinent information in accordance with local law. Depending on country requirements, the Investigator's name may also appear on the label. DAC HYP must not be used after the expiration date unless a written notification of an expiration date extension is provided by Biogen.

Autoinjector

The DAC HYP PFS is assembled inside a single-use, disposable autoinjector device.

The autoinjector label will include the DAC HYP product code "BIIB019," conditions for storage, Sponsor, and a caution statement. Depending on country requirements, the Investigator's name may also appear on the label. DAC HYP must not be used after the expiration date unless a written notification of an expiration date extension is provided by Biogen.

10.2. DAC HYP Preparation

Each DAC HYP PFS or autoinjector contains only one dose and is intended for SINGLE USE INJECTION ONLY. Any drug that remains in the PFS after injection must not be used for another dose or another subject.

After Week 12, subjects may choose to administer their DAC HYP dose at home, either by administering the injection themselves or by a designated caregiver. The subject or designated caregiver will be trained by clinic staff on the correct PFS injection technique prior to initiating at-home DAC HYP dosing.

Autoinjectors may be provided to selected sites and will be supplied injection-ready. Study personnel or subjects at these sites do not need to insert the PFS into the device. Study site personnel will receive appropriate autoinjector training from a Sponsor-designated trainer prior to initiation of autoinjector use.

CONFIDENTIAL

The information contained herein may not be used, disclosed, or published without the written consent of Biogen MA Inc.

10.3. DAC HYP Accountability

The study site must maintain accurate records demonstrating dates and amount of study treatment received, to whom dispensed (subject-by-subject accounting), any amount returned by subject, and accounts of any study treatment accidentally or deliberately destroyed.

Unless otherwise notified, all PFS and autoinjectors, both used and unused, must be saved for study treatment accountability. At the end of the study, a final reconciliation must be made between the amount of study treatment supplied, dispensed, and subsequently destroyed or returned to Biogen.

A written explanation will be provided for any discrepancies. After reconciliation, the Investigator must destroy or return to Biogen all unused study treatment PFS and autoinjectors as instructed by Biogen.

If any study treatment supplies are to be destroyed at the site, the Principal Investigator(s) must obtain prior approval by Biogen. The Principal Investigator(s) must notify Biogen, in writing, of the method, date, and location of destruction.

CONFIDENTIAL

The information contained herein may not be used, disclosed, or published without the written consent of Biogen MA Inc.

11. TREATMENT OF SUBJECTS

Biogen will provide DAC HYP (PFS or autoinjectors) to all study sites.

Refer to Section 10 (Study Treatment Management) for specifics on the preparation, storage, handling, disposal, and accountability of study treatment.

11.1. Study Treatment Schedule and Administration

All subjects will receive one DAC HYP 150 mg SC injection every 4 weeks.

DAC HYP will be administered by clinic staff at the monthly visits for the first 12 weeks of this study. After Week 12, administration of DAC HYP may occur in the clinic or at home (by the subject or by a designated caregiver) depending on subject preference. The subject or designated caregiver will be trained by clinic staff on the correct injection technique prior to initiating at-home DAC HYP dosing. **Subjects who are dosing at home must be instructed to not administer their monthly dose of DAC HYP until the study site has contacted them to authorize dosing. A window of ± 4 days applies to home dosing.**

Before a monthly dose of DAC HYP is given, LFT results from a prior test performed within the previous 32 days must be reviewed by the *Study Neurologist* or their backup. Study personnel should promptly inform the subject whether the monthly dose of DAC HYP should be administered or whether study treatment is to be withheld based on the dosing criteria defined in Section 11.7.2. Study personnel will document this communication with the subject. Subjects should administer DAC HYP as soon as permission has been given as per the dosing schedule. Subjects need to record the date and time of dosing in their diary if they are dosing at home.

11.2. Placebo or Reference Product Agents

Not applicable.

11.3. Treatment Precautions

Anaphylactic-like and hypersensitivity reactions following administration of proteins such as DAC HYP can occur. DAC HYP will be administered in the clinic under observation by qualified medical personnel for the first 12 weeks of this study. Subjects will be educated by the *Study Neurologist* or their back-up on the signs and symptoms of hypersensitivity reactions and instructed to contact the site if they experience any acute or delayed reactions post injection.

11.4. Treatment Compliance

Compliance with treatment dosing is to be monitored and recorded by study site staff.

After Week 12, subjects who choose to administer their DAC HYP dose at home will record treatment in a dosing diary. The diary will be reviewed periodically by study site staff and the Clinical Monitor throughout the study. Subjects who choose at-home administration will return used PFS or autoinjectors to the clinic at their scheduled clinic visits.

CONFIDENTIAL

The information contained herein may not be used, disclosed, or published without the written consent of Biogen MA Inc.

11.5. Concomitant Therapy

A concomitant therapy is any drug or substance administered from the Baseline/Entry Visit until completion of the study. A concomitant procedure is defined as any therapeutic intervention (e.g., surgery/biopsy, physical therapy) or diagnostic assessment (e.g., blood gas measurement, bacterial cultures) performed from the time the subject is enrolled in the study until the subject's final clinic visit.

11.5.1. Concomitant Therapies That are Prohibited

Concomitant treatment with any of the following is not allowed during the study, unless approved by the Biogen Medical Director(s) or the Advisory Committee, or as otherwise described in this protocol:

- Any alternative disease modifying MS drug treatment such as chronic immunosuppressant therapy or other immunomodulatory treatments (including, but not limited to: IFN- β , IFN- α , glatiramer acetate, cyclophosphamide, methotrexate, mycophenolate mofetil, mitoxantrone, cyclosporine, azathioprine, or related products).
- Any investigational product, including investigational symptomatic therapies for MS and investigational therapies for non-MS indications.
- Any monoclonal antibodies other than DAC HYP.
- Intravenous immunoglobulin (IVIg), plasmapheresis or cytappheresis, total lymphoid irradiation, or T-cell or T-cell receptor vaccination.
- Any systemic steroid therapy including, but not limited to, oral corticosteroids (e.g., prednisone) or periodic (e.g., monthly) treatment with IV methylprednisolone (IVMP), except for protocol-defined treatment of relapses as described in Section 14.6 or for limited, acute treatment of general medical conditions as per the discretion of *Study Neurologist*. Steroids that are administered by non-systemic routes (e.g., topical, inhaled) are allowed.
- Antineoplastic or chemotherapeutic agents, including, but not limited to, cyclophosphamide, methotrexate, azathioprine, cladribine, cytarabine, or flutamide.
- Valproic acid, carbamazepine, lamotrigine, or phenytoin. Subjects who have been taking 1 of these medications at a stable dose for at least 6 consecutive months may continue to receive the medication and may continue study treatment under this protocol. However, if any of these medications must be initiated or dose escalated, study treatment must be permanently discontinued as described in Section 11.8.

Subjects who have been treated with any of these medications (which have not been approved by the Biogen Medical Director[s]) for fewer than 6 consecutive months, or who take more than 1 of these medications, or who have had dose escalations within the past 6 months must do 1 of the following:

CONFIDENTIAL

The information contained herein may not be used, disclosed, or published without the written consent of Biogen MA Inc.

- Discontinue the medication (any agent used for <6 consecutive months must be discontinued). Subjects may use an alternative medication allowed by the protocol, if needed.
- Subjects taking more than 1 agent must reduce to ≤ 1 agent (any agent that is continued must have been taken for at least 6 consecutive months).
- In the case of dose escalation, revert to a previous dose that had been used for at least 6 months.
- Permanently discontinue study treatment.
- Isoniazid, propylthiouracil, or nimesulide. Subjects who currently take any of these medications must either change to an alternative medication allowed by the protocol or permanently discontinue study treatment.

Subjects who receive any of these restricted medications may be required to permanently discontinue study treatment as outlined in Section 11.8. Subjects who permanently discontinue study treatment will be allowed to receive IVMP as treatment for MS relapse while they are participating in the study, as described in Section 11.8.

11.5.2. Concomitant Therapies That Require Precaution

Caution should be used when administering drugs of known hepatotoxic potential, including non-prescription products, concomitantly with DAC HYP. Patients should be observed for signs and symptoms of hepatic dysfunction, particularly when DAC HYP is used concomitantly with other potentially hepatotoxic medicinal products. Use of the following medications is strongly discouraged during the study:

- Herbal or dietary supplements.
- Agents that have established risks of hepatotoxicity or serious rash according to labeling information (examples include, but are not limited to, amoxicillin/clavulanate, clarithromycin, ketoconazole, minocycline, nitrofurantoin, trimethoprim/sulfamethoxazole, diclofenac, sulfasalazine, amiodarone, methyldopa, nefazodone, halothane, and tizanidine). Alternatives to these therapies should be used whenever possible.

Symptomatic therapy, such as treatment for spasticity, depression, or fatigue is not restricted, but should be optimized as early as possible in an attempt to maintain consistent treatment for the duration of the study. Symptomatic therapies for spasticity that have established risks of hepatotoxicity are strongly discouraged for use during the study. Initiation of Fampridine-SR after enrollment is permitted, including when it is used in the acute management of protocol-defined relapse (as described in Section 14.6).

11.5.3. Concomitant Therapy Guidelines

Subjects should be instructed not to start taking any new medications, including non-prescribed medications, unless they have received permission from the Investigator. The use of live vaccines in humans concurrently treated with daclizumab has not been explored; therefore live vaccines should not be administered to MS subjects who are being treated with DAC HYP.

CONFIDENTIAL

The information contained herein may not be used, disclosed, or published without the written consent of Biogen MA Inc.

The use of concomitant therapies or procedures defined in this section must be recorded on the subject's case report form (CRF), according to instructions for CRF completion (Note: concomitant therapies in the parent study that continued at Study 205MS303 entry must be recorded on the CRF). AEs related to administration of these therapies or procedures must be documented on the appropriate CRF. For subjects who prematurely discontinue study treatment, all concomitant medications should be recorded throughout the remainder of the subject's participation in the study.

11.6. Continuation of Treatment

No further provisions are made for access to the study treatment. If DAC HYP is proven to be beneficial, all regulatory requirements regarding poststudy access will be met.

11.7. Treatment Schedule Modifications

Subjects who experience a significant change in their medical status (e.g., neurological worsening/suspected MS relapse, possible injection-site reaction, infection, cutaneous AE, fever, abdominal pain, persistent diarrhea, jaundice, nausea, vomiting, pruritus) must contact the *Study Neurologist* as soon as possible and no more than 48 hours after symptom onset. The subject should then be evaluated by the *Study Neurologist* within no more than 72 hours for physical and neurological assessments and further treatment recommendations if appropriate. These subjects should not administer additional DAC HYP until they have been evaluated by the *Study Neurologist* or their backup.

Unscheduled PK/■ Visit (Table 6) can be performed in subjects who have evidence of significant changes in their medical conditions (as assessed by the Investigator). This visit must be approved by the Biogen Medical Director in advance.

Additional treatment considerations for specific events are described below.

11.7.1. Infections

Subjects who have evidence of a clinically significant infection will be instructed to notify the *Study Neurologist* or their backup within 48 hours of onset, and scheduled dosing of DAC HYP may be withheld. If the subject's infection resolves within 2 weeks of the scheduled DAC HYP dose, the subject may receive the previously scheduled dose of DAC HYP at that time. If the infection has not resolved within the 2 weeks, dosing of DAC HYP will remain suspended, and the subject will miss dosing until the infection is resolved.

11.7.2. Elevated Liver Function Tests

Before a monthly dose of DAC HYP is given, LFT results from a prior test (performed within the previous 32 days) must be reviewed by the *Study Neurologist* or their backup, and must be within the protocol-required limits shown below (LFT procedures are described in Section 14.4.3).

If a subject develops clinical signs or symptoms suggestive of hepatic dysfunction (e.g., unexplained nausea, vomiting, abdominal pain, fatigue, anorexia, or jaundice and/or dark

CONFIDENTIAL

The information contained herein may not be used, disclosed, or published without the written consent of Biogen MA Inc.

urine), promptly measure serum transaminases and interrupt or discontinue treatment with DAC HYP, as appropriate.

Table 8 summarizes how subjects with elevated LFTs will be managed during the study.

11.7.2.1. ALT/SGPT or AST/SGOT >3 to ≤5×ULN

In subjects with alanine aminotransferase/serum glutamic pyruvic transaminase (ALT/SGPT) or aspartate aminotransferase/serum glutamic oxaloacetic transaminase (AST/SGOT) >3 to ≤5×ULN and total bilirubin ≤2×ULN, the following should be performed:

- Study treatment *must be temporarily suspended*.
- LFT elevation should be confirmed as soon as possible but no later than 1 week by a repeat test performed at the central laboratory.
- Tests are repeated weekly until both ALT/SGPT and AST/SGOT are <2×ULN.
- After a temporary suspension, dosing of DAC HYP may be resumed when ALT/SGPT and AST/SGOT are <2×ULN provided that the criteria for permanent discontinuation have not been met (see Section 11.8).

In subjects with ALT/SGPT or AST/SGOT >3 to ≤5×ULN and total bilirubin >2×ULN, the following should be performed:

- Study treatment must be withheld.
- LFT elevation should be confirmed as soon as possible but no later than 1 week by a repeat test performed at the central laboratory.
- If the elevation is confirmed on repeat testing, study treatment *must be permanently discontinued*. Otherwise, follow the guidelines in Section 11.7.2.4.

In addition to these conditions, study treatment must be temporarily suspended and managed per the guidelines in Section 11.7.2.4 if a subject develops any other clinically significant hepatic condition in the opinion of the Investigator, including jaundice.

11.7.2.2. ALT/SGPT or AST/SGOT >5×ULN

In subjects with an ALT/SGPT or AST/SGOT >5×ULN, regardless of total bilirubin level, the following should be performed:

- Study treatment must be withheld.
- LFT elevation should be confirmed as soon as possible but no later than 1 week by a repeat test performed at the central laboratory.
- If the elevation of >5×ULN is confirmed on repeat testing, study treatment *must be permanently discontinued*. Otherwise, follow the guidelines in Section 11.7.2.4.

11.7.2.3. Second Temporary Suspension Due to Elevated LFTs

If a subject has treatment suspended for an LFT elevation and has also had a prior treatment suspension for an LFT elevation during DAC HYP use, DAC HYP must be permanently

CONFIDENTIAL

The information contained herein may not be used, disclosed, or published without the written consent of Biogen MA Inc.

discontinued unless an alternative explanation for the LFT elevation unrelated to DAC HYP use is clearly identified by the Investigator.

11.7.2.4. Management Guidelines Following Temporary Suspension or Permanent Discontinuation

All subjects with elevated LFTs (**ALT/SGPT or AST/SGOT >3×ULN**) should be managed per the guidelines below.

- Study treatment must be temporarily suspended and LFT elevation should be confirmed as soon as possible but no later than 1 week by a repeat test performed at the central laboratory. In cases where LFTs cannot be performed via the central laboratory, repeat LFT results from a local laboratory can be used for confirmation.
- After a temporary suspension, dosing of DAC HYP may be resumed when ALT/SGPT and AST/SGOT are <2×ULN provided that the criteria for permanent discontinuation have not been met (see Section 11.8).
- For subjects that have had DAC HYP treatment suspended for >8 weeks due to elevated LFTs, Investigators should consider whether subjects should permanently discontinue treatment with DAC HYP in order to allow treatment with another disease-modifying therapy and minimize the risk of return of MS disease activity. Such decisions are at the discretion of the Investigators and their assessment of risks and benefits.
- All subsequent testing after a temporary treatment suspension or permanent discontinuation is required to be performed centrally *at least weekly* until the LFT elevation is <2×ULN.
- Monitoring of LFT elevations will occur for up to 6 months after the last DAC HYP dose has been administered. If after 6 months the LFT remains elevated at ≥2×ULN, the Investigator or health care professional should continue to monitor the LFT as clinically appropriate; any relevant follow-up data should be reported to the Sponsor as a spontaneous report.
- A careful review of all concomitant medications must be documented. The Investigator should consider discontinuation of all potential hepatotoxic medications. All recently started or non-essential concomitant medications should be suspended until the LFT elevation is <2×ULN.
- An Unscheduled Hepatic Assessment Visit as soon as possible but within 1 week should be performed in the event of permanent discontinuation due to elevated LFTs (see Table 6).
- Subjects should be referred to a hepatic specialist if medically indicated. In consultation with the hepatic specialist, a full evaluation of alternative causes of liver injury should be performed. Additional hepatic studies should be performed according to local standard of care. The central laboratory may be utilized for additional hepatic testing per Investigator request. If testing for viral hepatitis is negative, LFT elevations are not improving, DAC HYP is suspected as the cause of

CONFIDENTIAL

The information contained herein may not be used, disclosed, or published without the written consent of Biogen MA Inc.

the LFT elevation, and there are no known contraindications for corticosteroids, then, in continued consultation with the hepatic specialist, empiric treatment with systemic corticosteroids should be considered.

Table 8: Summary of Management of Subjects With Elevated Liver Function Tests

Total Bilirubin	Serum Transaminases		
	ALT/SGPT or AST/SGOT >3 to ≤5×ULN	ALT/SGPT or AST/SGOT >5×ULN	Second Temporary Suspension Due to Elevated ALT/SGPT or AST/SGOT
≤2×ULN	Temporarily suspend dosing ¹ Weekly LFT until both ALT/SGPT and AST/SGOT are <2×ULN	Withhold dosing ² Repeat test as soon as possible but no later than 1 week after the elevation If confirmed, permanently discontinue study treatment. Otherwise, follow the guidelines in Section 11.7.2.4.	Withhold dosing ² Repeat test as soon as possible but no later than 1 week after the elevation If confirmed, permanently discontinue study treatment. Otherwise, follow the guidelines in Section 11.7.2.4.
>2×ULN	Withhold dosing ² Repeat test as soon as possible but no later than 1 week after the elevation If confirmed, permanently discontinue study treatment. Otherwise, follow the guidelines in Section 11.7.2.4.	As above	As above

ALT = alanine aminotransferase; AST = aspartate aminotransferase; LFT = liver function test; SGOT = serum glutamic oxaloacetic transaminase; SGPT = serum glutamic pyruvic transaminase; ULN = upper limit of normal.

¹ Subjects should be managed according to the following guidelines: LFT elevation should be confirmed as soon as possible but no later than 1 week; LFT is required to be performed *at least weekly* until the LFT elevation is <2×ULN; dosing of DAC HYP may be resumed when ALT/SGPT, AST/SGOT, and bilirubin are <2×ULN, provided that the criteria for permanent discontinuation have not been met; a careful review of all concomitant medications must be documented; and if treatment is permanently discontinued, subjects should be referred to a hepatic specialist if medically indicated.

² Subjects should be managed according to the following guidelines: LFT elevation should be confirmed as soon as possible but no later than 1 week; LFT is required to be performed *at least weekly* until the LFT elevation is <2×ULN; an Unscheduled Hepatic Assessment Visit is performed as soon as possible but within 1 week of the elevation; a careful review of all concomitant medications must be documented; and if treatment is permanently discontinued, subjects should be referred to a hepatic specialist if medically indicated.

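### Sections 11.7.2.1 and 11.7.2.4 allow DAC HYP to restart on ALT and AST alone, while Table 8 footnote 1 also requires bilirubin <2×ULN for the same subjects

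*Protocol*

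**What the plan says.** All the text concerned stands in the protocol text in which Table 8 is the liver-test management table. The other protocol texts in the file use that table number for vital signs and play no part here.

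- **Section 11.7.2** introduces the table: "Table 8 summarizes how subjects with elevated LFTs will be managed during the study".
- **Section 11.7.2.1**, for ALT or AST >3 to ≤5×ULN with bilirubin ≤2×ULN, requires suspension and allows restart once ALT and AST are <2×ULN, if no permanent-stop criterion is met. On monitoring it says "Tests are repeated weekly until both ALT/SGPT and AST/SGOT are <2×ULN".
- **Section 11.7.2.4**, for all subjects with ALT or AST >3×ULN, repeats the restart rule: "After a temporary suspension, dosing of DAC HYP may be resumed when ALT/SGPT and AST/SGOT are <2×ULN". Bilirubin is not named.
- **Table 8, first cell** (the 11.7.2.1 subjects just described) ends testing the same way, "Weekly LFT until both ALT/SGPT and AST/SGOT are <2×ULN", and carries footnote 1.
- **Table 8, footnote 1** adds an analyte: "dosing of DAC HYP may be resumed when ALT/SGPT, AST/SGOT, and bilirubin are <2×ULN".
- **Table 8, bilirubin >2×ULN row**: the first cell carries footnote 2 and the other two refer to the cells above them. The instruction is "If confirmed, permanently discontinue study treatment. Otherwise, follow the guidelines in Section 11.7.2.4". Footnote 2 goes from the timing of the hepatic visit straight to the medication review ("within 1 week of the elevation; a careful review of all concomitant medications must be documented"), with no restart condition.

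**The concern.** A summary table and the text it summarizes should give sites one rule. Here they give two for the same subjects, and they differ on total bilirubin, which is already part of the liver panel. Two sites with identical results could reach opposite dosing decisions, and each could cite the protocol.

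The placement is also the reverse of what one would expect. The bilirubin condition is attached to subjects whose bilirubin was ≤2×ULN at onset. Those who began above 2×ULN and were not confirmed go to a rule that does not mention it.

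The stake is dosing safety. Section 5.1 describes transaminase elevations and serious hepatic events as part of the drug's safety profile in Study 205MS301. Under section 11.1 home doses wait for site authorization based on the liver results, so the written restart rule decides whether the injection is given.

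**Working it through.** No figure in the plan needs reproducing, since the check is one of consistency. The rules are set side by side and an example subject is followed through them.

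**Step 1. Restart conditions**

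| Place | Subjects covered | Condition for restart |
|---|---|---|
| 11.7.2.1 | ALT/AST >3 to ≤5×ULN, bilirubin ≤2×ULN | ALT and AST <2×ULN |
| 11.7.2.4 | all with ALT/AST >3×ULN | ALT and AST <2×ULN |
| Table 8 footnote 1 | ALT/AST >3 to ≤5×ULN, bilirubin ≤2×ULN | ALT, AST and bilirubin <2×ULN |
| Table 8 footnote 2 | the other cells | none; unconfirmed cases go to 11.7.2.4 |

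The first and third rows cover the same subjects and disagree.

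**Step 2. Does the proviso on permanent discontinuation close the gap?** Both the body text and footnote 1 make restart subject to the stopping criteria. Section 11.8 has three liver criteria: ALT or AST >5×ULN, confirmed; ALT or AST >3×ULN with concomitant bilirubin >2×ULN, confirmed; and a second suspension without a clear alternative explanation. The only one that names bilirubin needs ALT or AST >3×ULN at the same time. At the moment of restart ALT and AST are <2×ULN, so a raised bilirubin then cannot newly meet it.

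**Step 3. Example.** The values are assumed, in multiples of ULN, for a first suspension with AST no higher than ALT throughout.

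| Day | ALT | Bilirubin | ALT >3 and bilirubin >2 together? |
|---|---|---|---|
| 0 | 4.0 | 1.6 | no (1.6 ≤ 2) |
| 7 | 2.6 | 2.3 | no (2.6 ≤ 3) |
| 14 | 1.8 (AST 1.8) | 2.3 | no (1.8 ≤ 3) |

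- 11.8: ALT is never >5, the joint elevation never occurs, and there is no second suspension. No liver criterion for stopping is met.
- 11.7.2.1 and 11.7.2.4 on day 14: ALT 1.8 <2 and AST 1.8 <2, so restart is permitted.
- Footnote 1 on day 14: bilirubin 2.3 is not <2, so restart is not permitted.

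The same results give opposite answers.

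**Step 4. Subjects starting with bilirubin >2×ULN.** Take day 0 ALT 4.0 and bilirubin 2.5, then a repeat with ALT and AST 1.8 and bilirubin still 2.5 (assumed). If confirmation means that the joint elevation recurs, it is not confirmed. Table 8 and 11.7.2.1 then send the subject to 11.7.2.4, where ALT and AST at 1.8 suffice for restart. This example depends on that reading of confirmation; the one in Step 3 does not.

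**The case against.** **The footnote may be the outlier.** Two body sections name only ALT and AST, and the cell that footnote 1 annotates ends testing on them too. Deleting bilirubin from the footnote would also restore consistency. This stands as logic: the text does not show which rule was intended. The stricter rule is preferred here because it is already written in the protocol and needs no new test.

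**The body rule is permissive.** A site that follows footnote 1 breaches nothing in 11.7.2.1 or 11.7.2.4. That is true, but a site that redoses under 11.7.2.4 can equally cite the protocol.

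**The pre-dose check.** A reader might infer that the pre-dose review has no bilirubin limit at all once ALT and AST have fallen. That goes too far. Section 14.1 includes total bilirubin in the results reviewed, section 11.7.2 requires them to be within the limits that follow, and footnote 1 is such a limit for its own cell. The fault is that the body text contradicts it and that subjects sent to 11.7.2.4 from the other cells have no equivalent.

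**Weekly testing.** A reader might infer that monitoring always stops on ALT and AST. Section 11.7.2.4 and both footnotes also require testing at least weekly until the liver-test elevation is <2×ULN, and the panel includes total bilirubin. The stopping point is therefore ambiguous, and in any case this wording governs testing and not restart.

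**Confirmation in 11.8.** The confirmed finding could be read as the bilirubin elevation alone. On that reading the subject in Step 4 stops permanently. This limits the second route but not the first.

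**Other safeguards.** Footnote 2 requires a hepatic assessment visit within a week. Section 11.7 holds dosing in subjects with symptoms such as jaundice until they are evaluated. Section 11.7.2.1 suspends for "any other clinically significant hepatic condition in the opinion of the Investigator, including jaundice", and 11.8 leaves the Investigator free to stop. These reduce the risk, but they rest on clinical judgement, and the 11.7.2.1 suspension itself leads back to 11.7.2.4.

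**Conclusion.** The contradiction is real, and it lies within one protocol text. For subjects with ALT or AST >3 to ≤5×ULN and bilirubin ≤2×ULN at onset, the body text permits a restart that footnote 1 withholds whenever ALT and AST have fallen below 2×ULN and bilirubin has not. For subjects who start above 2×ULN and are not confirmed, the governing section has no bilirubin condition.

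The size cannot be given as a frequency, because the protocol contains no count of such subjects and the examples use assumed values. A reader might take the number of Table 8 cells without the bilirubin condition as a measure of risk. It is not: the default in those cells is permanent discontinuation on confirmation, and a second suspension normally ends treatment. Nor do the documents support a claim that the primary endpoint or a planned analysis is affected. This is a dosing-safety inconsistency that should be corrected.

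**What to change.** In sections 11.7.2.1 and 11.7.2.4, require ALT, AST and total bilirubin all <2×ULN before restart, and continue weekly liver tests until all three are met. This matches footnote 1 and, through the cross-reference to 11.7.2.4, reaches the cells that carry footnote 2. Align the weekly-test line in the first cell of Table 8. No suspension or permanent-stop threshold changes, and no new test is needed.

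The cost is a longer hold and more weekly tests when bilirubin falls more slowly than ALT and AST. A subject with stable bilirubin ≥2×ULN from an unrelated cause could not restart at all, and after more than 8 weeks of suspension 11.7.2.4 asks the Investigator to consider permanent discontinuation. The amended rule should therefore allow an exception when an alternative cause of the raised bilirubin is documented. If the sponsor intended restart on ALT and AST alone, footnote 1 should be changed to say so and the choice justified.
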